4.4.1 Management and Dose Modifications for Skin Toxicities

Cutaneous AEs have been observed in subjects receiving dabrafenib, trametinib or both therapies in combination. See IBs for further information.[4, 5] In addition to dose modifications detailed below, please also see section 11.5 (Appendices) for supportive care measures for rash. See section 6.0; dermatologic evaluations will take place at baseline, during treatment and follow-up.

4.4.1.1 Rash

Rash is a frequent AE observed in subjects receiving trametinib, dabrafenib, or the combination of both therapies. See section 11.5 (Appendices) for recommended rash prophylaxis for the first 6 weeks of study treatment. Guidelines for management and dose reduction for rash considered related to study treatment are provided in the table below.

CTCAE Grade	Management of Rash	Action and Dose Modification for Dabrafenib and Trametinib
1	Initiate prophylactic regimen if not already started (recommended for the first 6 weeks of treatment (see section 11.5 (appendices)). Treat with moderate strength topical steroid.* Reassess after 2 weeks	Continue current dose. If rash does not recover to baseline within 2 weeks despite best supportive care, reduce study treatment by one dose level
2	Initiate prophylactic regimen if not already started (recommended for the first 6 weeks of treatment (see section 11.5 (appendices)). Treat with moderate strength topical steroid.* Reassess after 2 weeks	Reduce study treatment by at least one dose level. If toxicity resolves to \leq Grade 1 within 2 weeks, increase dose to previous dose level. If no recovery to \leq Grade 1 within 2 weeks, interrupt study treatment until \leq Grade 1. When restart, restart at the reduced dose level.
≥ 3	Treat with moderate strength topical steroid * PLUS oral methylprednisolone dose pack. Consider obtaining dermatology consultation	Interrupt study treatment until rash recovers to \leq Grade 2. Restart with study treatment reduced by one dose level. May consider escalating study treatment to previous dose level if no rash is evident 4 weeks after restarting treatment. If no recovery to grade ≤ 2 within 4 weeks, permanently discontinue study treatment.

*eg, hydrocortisone 2.5% cream or fluticasone propionate 0.5% cream

4.4.2 Malignancies

4.4.2.1 Squamous Cell Carcinoma (SCC)

Cutaneous SCC (cuSCC; include those classified as keratoacanthoma or mixed keratoacanthoma subtype) have been observed in subjects treated with dabrafenib and the combination of dabrafenib and trametinib (see dabrafenib and trametinib combination IB)[6]. Approximately 70 % of events occurred within the first 12 weeks of treatment with a median time to onset of 8 weeks. These treatment-related cutaneous SCC should be surgically removed according to institutional practice. Dose modifications or interruptions of the study treatment are not required for cutaneous SCC. Occurrence of cutaneous SCC must be reported as an SAE (see Section 7.3.3).

Patients should be instructed to immediately inform their physician if new lesions develop.

4.4.2.2 New Primary Melanoma

New primary melanomas have been reported in patients treated with dabrafenib. These were identified primarily within the first 5 months of therapy and did not require treatment modification other than excision. Monitoring for skin lesions should occur as described for cuSCC.

4.4.2.3 Non-Cutaneous Malignancies

In vitro experiments have demonstrated paradoxical activation of MAP-kinase signalling in BRAF wild type cells with RAS mutations when exposed to BRAF inhibitors, which may lead to increased risk of non-cutaneous malignancies in patients treated with dabrafenib. Cases of RAS-driven malignancies have been seen with BRAF inhibitors. Patients should be monitored as clinically appropriate. New non-cutaneous malignancies should be reported as a SAE.

4.4.2.4 Palmar-plantar erythrodysesthesia syndrome (PPES; also known as Hand-Foot-Skin-Reaction (HFSR))

Episodes of HFSR have been observed in subjects receiving dabrafenib. Guidelines for management of HFSR, and dose modifications for study treatment for HFSR potentially related to study treatment are listed in the table below. Management can differ from the guidelines below based on the clinical judgment of the investigator. The investigator should contact the overall PI to discuss skin toxicity as needed. Dermatologic exams should be performed by the Investigator as noted in the Time and Events Table, or may be referred to a dermatologist, at the discretion of the investigator. If possible, the same physician should perform each exam for the duration of the study (i.e. if the subject is referred to a dermatologist for the screening exam, the dermatologist should do all follow up dermatologic assessments) to ensure consistency between evaluations. A full-body skin examination and a removal of pre-existing calluses and keratotic skin is recommended prior to initiation of study treatment.

Life-style changes recommended for any grade of HFSR include the following:

- Reduce exposure of hands and feet to hot water,
- Avoid traumatic activity including vigorous exercise especially in the first 4 weeks after start of study treatment
- Avoid constrictive footwear
- Avoid excessive friction on the skin, when applying topical treatments
- Wear thick cotton socks and gloves, and shoes with padded insoles

Symptomatic treatments suggested for any grade of HFSR include the following:

- Use moisturizing creams frequently and especially on hands and feet
- Consider topical keratolytics: urea 20-40 % cream, or salicylic acid 6%, or tazarotene 0.1% cream, or fluorouracil 5% cream
- For erythematous areas: clobetasol propionate 0.05% ointment

- For pain: topical lidocaine 2%, and / or systemic pain medication such as nonsteroidal anti-inflammatory drugs, codeine, and pregabalin

Symptoms usually resolve within 2-4 weeks of treatment cessation.

CTCAE Grade	Management of HFSR	Action and Dose Modification for HFSR for Dabrafenib and Trametinib
1	Lifestyle changes recommended Initiate symptomatic treatment if clinically appropriate	Continue study treatment at current dose level
2	Lifestyle changes recommended Initiate symptomatic treatment	Interrupt study treatment until recovery to \leq grade 1 Recovery to \leqgrade 1 within 7 days: Restart study treatment at previous dose level No recovery to grade \leq1 within 7 days or \geq 2nd occurrence: restart with study treatment reduced by one dose level^a
3	Lifestyle changes recommended Initiate symptomatic treatment Consider consulting dermatologist	Interrupt study treatment until recovery to \leq grade 1 Restart with study treatment reduced by one dose level^a If 3 rd occurrence, discontinue study treatment permanently
^a Escalation of study treatment to the previous dose level is allowed if no HFSR is observed in the 4 weeks subsequent to dose reduction.		

4.4.3 Management and Dose Modifications for Cardiac Toxicities

Cardiovascular adverse events have been seen in subjects receiving either dabrafenib, trametinib or both in combination. (See the IBs for additional information[4-6].

4.4.3.1 Hypertension

Increases in blood pressure have been observed in subjects receiving trametinib. Recommendations for blood pressure monitoring and management are provided below.

Monitoring of Hypertension

All blood pressure assessments should be performed under the following optimal conditions for the study subject:

- has been seated with back support, ensuring that legs are uncrossed and flat on the floor
- is relaxed comfortably for at least 5 minutes
- restrictive clothing has been removed from the cuff area and the right cuff size has been selected

- arm is supported so that the middle of the cuff is at heart level
- remains quiet during the measurement

In subjects with an initial blood pressure reading within the hypertensive range, a second reading should be taken at least 1 minute later, with the 2 readings averaged to obtain a final blood pressure measurement. The averaged value should be recorded in the eCRF.

Persistent hypertension is defined as an increase of systolic blood pressure (SBP) > 140 mm Hg and/or diastolic blood pressure (DBP) > 90 mm Hg in three consecutive visits with blood pressure assessments from two readings collected as described above. Visits to monitor increased blood pressure can be scheduled independently from the per-protocol visits outlined in the Time and Events Table (see section 6.1). Ideally, subsequent blood pressure assessments should be performed within one week.

Asymptomatic hypertension is defined as an increase of SBP to >140 mm Hg and/or DBP >90 mm Hg in the absence of symptoms including headache, light-headedness, vertigo, tinnitus, episodes of fainting or other symptoms indicative of hypertension that resolve after the blood pressure is controlled within the normal range.

Management of Hypertension

For subjects experiencing an increase in systolic and/or diastolic blood pressure that is persistent and may be associated with the study treatment, recommendations for the clinical management of hypertension are described below:

Hypertension	Action and Dose Modification for Dabrafenib and Trametinib
(Scenario A) Asymptomatic and persistent (terms defined above) SBP of >140 and <160 mmHg, or DBP >90 and <100 mmHg, or Clinically significant increase in DBP of 20 mmHg (but still below 100 mmHg).	Continue study treatment at the current dose Adjust current or initiate new antihypertensive medication Titrate antihypertensive medication(s) during the next 2 weeks as indicated to achieve well-controlled ^a BP If BP is not well controlled within 2 weeks, consider referral to a specialist and go to scenario (B).
(Scenario B) Asymptomatic SBP >160 mmHg, or DBP >100 mmHg, or Failure to achieve well-controlled BP within 2 weeks in Scenario A	Interrupt study treatment if clinically indicated Adjust current or initiate new antihypertensive medication(s) Titrate antihypertensive medication(s) during the next 2 weeks as indicated to achieve well-controlled BP ^a Once BP is well controlled ^a , restart study treatment reduced by one dose level^c
(Scenario C) Symptomatic ^b hypertension or Asymptomatic and persistent (term defined above) SBP ≥160 mmHg, or DBP ≥100 mmHg, despite antihypertensive medication and dose reduction of study treatment	Interrupt study treatment Adjust current or initiate new antihypertensive medication(s) Titrate antihypertensive medication during the next 2 weeks as indicated to achieve well-controlled BP ^a Referral to a specialist for further evaluation and follow-up is recommended Once BP is well controlled ^a , restart study treatment reduced by one dose level
Scenario D) Refractory hypertension unresponsive to above interventions or hypertensive crisis.	Permanently discontinue study treatment Continue follow-up per protocol.
^a Well-controlled blood pressure defined as SBP ≤140 mm Hg and DBP ≤90 mm Hg in two separate readings during up to three consecutive visits. ^b Symptomatic hypertension defined as hypertension aggravated by symptoms (e.g., headache, light-headedness, vertigo, tinnitus, episodes of fainting) that resolve after the blood pressure is controlled within the normal range. ^c Escalation of trametinib to previous dose level can be considered if BPs remain well-controlled for 4 weeks after restarting of trametinib. Approval from study PI is required.	

4.4.3.2 QTc

Guidelines for dose modification and stopping criteria due to QTC-prolongation are provided in the following table. In studies to date, dabrafenib and trametinib do not exhibit an apparent potential to alter the QTc interval. The proportion of subjects with QTc interval >60 msec increases from baseline was higher in Part C

of study BRF113220 as compared to trametinib ISS and the dabrafenib ISS populations (13% compared to 3% and 3% respectively). [6]

QTc-Prolongation ^a	Action and Dose Modification for Dabrafenib and Trametinib
QTc≥501 msec OR uncorrected QT>600 msec OR QTc>530 msec for subjects with bundle branch block	Interrupt study treatment until QTc prolongation resolves to grade 1 or baseline Test serum potassium, calcium, phosphorus and magnesium. If abnormal, correct per routine clinical practice to within normal limits Review concomitant medication usage for a prolonged QTc Restart at current dose level ^b If event recurs, permanently discontinue study treatment
^a Based on average QTc value of triplicate ECGs. For example, if an ECG demonstrates a prolonged QT interval, obtain two or more ECGs over a brief period, and then use the averaged QTc values of the three ECGs to determine if study treatments should be interrupted or discontinued. ^b If the QTc prolongation resolves to grade 1 or baseline, the subject may resume study treatment if the site investigator and study PI agree that the subject will benefit from further treatment.	

4.4.3.3 Reduced Left Ventricular Ejection Fraction

Decreases of the left ventricular ejection fraction (LVEF) have been observed in subjects receiving trametinib monotherapy and in combination with dabrafenib. Therefore, ECHOs must be performed to assess cardiac ejection fraction at regular intervals. ECHOs should be performed at baseline and at follow-up visit(s) See Time and Events table (section 6.1 for timing of follow-up ECHOs. Dose modification guidance and stopping criteria for LVEF decrease are provided in the table below.

LVEF-drop (%) or CTCAE grade	Action and Dose Modification

Asymptomatic* Absolute decrease of $\geq 10\%$ in LVEF compared to baseline and ejection fraction below the institution's LLN
 
*NOTE: symptoms may include dyspnea, orthopnea, and other signs and symptoms of pulmonary congestion and edema
	
Interrupt study treatment (both drugs) and repeat ECHO within 2 weeks. If LVEF has not recovered in 2 weeks, repeat 2 weeks later.
 
If the LVEF recovers within 4 weeks (defined as LVEF \geqLLN and absolute decrease $\leq 10\%$ compared to baseline):
 
 • Restart with trametinib reduced by one dose level in consultation with study PI • Restart dabrafenib at previous dose level • Repeat ECHO 2, 4, 8 and 12 weeks after re-start; continue in intervals of 12 weeks thereafter 
If LVEF does not recover within 4 weeks
 
 • Consult with cardiologist • Permanently discontinue trametinib • Report as SAE • Repeat ECHO after 2, 4, 8, 12, and 16 weeks or until resolution • Consult with study PI regarding restart of dabrafenib once LVEF recovers

Symptomatic* Grade 3: resting LVEF 39-20% or $>20\%$ absolute reduction from baseline
	
Permanently discontinue trametinib. Discontinue dabrafenib.
 
Report as SAE
 
Consult with cardiologist

Symptomatic Grade 4: resting LVEF $<20\%$
	
Repeat ECHO after 2, 4, 8, 12, and 16 weeks or until resolution
 
Consult with study PI regarding restart of dabrafenib once LVEF recovers

4.4.4 Management and Dose Modifications for Visual Changes

Episodes of visual changes have been observed in subjects receiving dabrafenib, trametinib or the combination of both therapies. Ocular adverse events are known to be related to trametinib. The causal relationship between a change in vision and the study treatment should be carefully explored and an ophthalmologist should be consulted. However, if the visual changes are clearly unrelated to study treatment (e.g., allergic conjunctivitis), then monitor closely as it may be reasonable to defer ophthalmic examination. Treatment with dabrafenib has been associated with the development of uveitis, including iritis. Monitor patients for visual signs and symptoms (such as, change in vision, photophobia and eye pain) during therapy. For adverse events of uveitis, no dose modifications are required as long as effective local therapies can control ocular inflammation. If uveitis does not respond to local ocular therapy, interrupt dabrafenib and hold until resolution of ocular inflammation. Then restart dabrafenib reduced by one dose level.

Special attention should be given to retinal problems (e.g., retinal pigment epithelium detachments (RPED)) or retinal vein abnormalities (e.g., RVO).

Refer to section 11.1 (Appendices) for grading of visual changes.

If visual changes develop, an eye exam is indicated. The exam will include best corrected visual acuity, tonometry, slit lamp biomicroscopic examination, visual field examination, and dilated indirect funduscopy with special attention to retinal abnormalities. Optical coherence tomography is strongly recommended at scheduled visits, and if retinal abnormalities are suspected. Other types of ancillary testing including color fundus photography and fluorescein angiography are also recommended if clinically indicated.

CTCAE Grade ^a	Management of Visual Changes	Action and Dose Modification for Dabrafenib and Trametinib
1 ^b	Consult ophthalmologist within 7 days of onset Exclude RPED, and RVO Consult retinal specialist in case of RPED or RVO Continue follow up examination(s) by retinal specialist for RPED and RVO	If dilated fundus examination cannot be performed within 7 days of onset, interrupt study treatment until RPED and RVO can be excluded by retina specialist/ophthalmologist and symptoms resolve If RPED and RVO excluded, restart study treatment at same dose level RPED suspected or diagnosed and Grade 1 (asymptomatic; clinical or diagnostic observations only)^a : Continue treatment with retinal evaluation monthly until resolution. If it worsens follow instructions for grade. ^a RVO: Permanently discontinue study treatment and report as SAE
2 and 3	Consult ophthalmologist immediately Interrupt study treatment	If RPED and RVO excluded, restart study treatment at same dose level. If RPED diagnosed (Symptomatic with mild to moderate decrease in visual acuity; limiting instrumental ADL) ^a , continue retinal evaluation monthly until resolves to ≤Grade 1. At that point, restart study treatment reduced by one dose level. RVO: Permanently discontinue study treatment and report RVO as SAE
4	Consult ophthalmologist immediately Interrupt study treatment	If RPED and RVO excluded, may consider restarting study treatment at same or reduced dose. If RVO or RPED diagnosed, permanently discontinue study treatment and report as SAE.
^a Refers to CTCAE Version 4.0 'Eye disorders – Other, specify' (also see section 11.1 in Appendices); RPED graded as per CTCAE v4 "Retinopathy" ^b If visual changes are clearly unrelated to study treatment (e.g., allergic conjunctivitis), monitor closely but ophthalmic examination is not required.		

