4.4.8 Management and Dose Modification Guidelines for Therapy-related Pyrexia

Pyrexia is defined as $\geq 38.5^{\circ}\text{C}$ or 101.3°F . Episodes of pyrexia have been observed in subjects receiving dabrafenib monotherapy and is increased in incidence and severity in subjects receiving dabrafenib in combination with trametinib. (Pyrexia is also a side effect of trametinib, but is less frequent than that associated with dabrafenib-see section 5.1.5). [6] In a minority of cases the pyrexia was accompanied by symptoms such as severe chills, dehydration, hypotension, dizziness or weakness. Pyrexia accompanied by hypotension, dehydration requiring IV fluids, or severe rigors/chills should be reported as an SAE (see section 7.3.3). Subjects should be instructed on the importance of immediately reporting febrile episodes. In the event of a fever, the subject should be instructed to take non-steroidal anti-pyretics (e.g., ibuprofen), acetaminophen or other suitable anti-pyretic medication as appropriate to control fever. The use of oral corticosteroids should be considered in those instances in which anti-pyretics are insufficient. In subjects experiencing pyrexia associated with rigors, severe chills, dehydration, hypotension, etc., renal function should be monitored carefully.

For each episode of pyrexia (defined above), a thorough clinical examination (including blood pressure) for signs and symptoms of infection or hypersensitivity is required; laboratory work-up should include full blood count, electrolytes, creatinine, BUN, CRP, liver function tests, blood culture, and urine culture. For subjects experiencing pyrexia complicated by rigors, severe chills, etc., a clinical evaluation and laboratory work-up is mandatory for each event; anti-pyretic treatment should be started immediately at the first occurrence and prophylactic anti-pyretic treatment is recommended. This prophylactic treatment may be discontinued after 3 days in the absence of pyrexia.

Oral hydration should be encouraged in subjects without evidence of dehydration. Intravenous hydration is recommended in subjects experiencing pyrexia complicated by dehydration/hypotension.

Pyrexia Management	Action and Dose Modification

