4.4.9.1 Definition of Liver Chemistry Stopping Criteria

Trametinib and dabrafenib will be permanently discontinued when any of the stopping criteria (1-5) listed below is met.

1. Alanine aminotransferase (ALT) $\geq 3x$ upper limit of normal (ULN) **and** bilirubin $\geq 2x$ ULN (>35% direct bilirubin) or ALT $\geq 3x$ ULN **and** international normalized ratio [INR] >1.5, if INR measured.
 - a. INR measurement is not required and the threshold value stated will not apply to subjects receiving anticoagulants
 - b. Serum bilirubin fractionation should be performed if testing is available. If testing is unavailable, discontinue study treatment, and **record presence of detectable urinary bilirubin on dipstick** indicating direct bilirubin elevations and suggesting liver injury.
NOTE: Any case that meets these criteria and is considered to be drug related is considered to be an SAE by GSK. This is called "Hy's Law." If a Hy's Law case occurs but there is a potential explanation for it other than drug, please consult with the Study PI.
2. ALT $\geq 8x$ ULN.
3. ALT $\geq 5x$ ULN but <8 x ULN persists for ≥ 2 weeks.
4. ALT $\geq 3x$ ULN if associated with the appearance or worsening of symptoms of hepatitis or hypersensitivity such as fatigue, nausea, vomiting, right upper quadrant pain or tenderness, fever, rash or eosinophilia.
5. ALT $\geq 5x$ ULN but <8 x ULN and cannot be monitored weekly for >2 weeks

4.4.9.2 Follow-up Action if Liver Chemistry Stopping Criteria are Met:

- **Immediately discontinue subject from study treatment**
- Report the event to GSK **within 24 hours** of learning of its occurrence (see section 7.3.3).
- Complete the liver event and SAE electronic case report form (eCRF) within Oncore® if the event also meets the criteria for an SAE:
 - All events of ALT $\geq 3x$ ULN **and** bilirubin $\geq 2x$ ULN (>35% direct bilirubin) **or** ALT $\geq 3x$ ULN and INR >1.5, if INR measured, termed 'Hy's Law', **must be reported as an SAE**
 - NOTE: if serum bilirubin fractionation is not immediately available, study treatment should be discontinued if ALT $\geq 3x$ ULN **and** bilirubin $\geq 2x$ ULN. Serum bilirubin fractionation should be performed if testing is available. If testing is unavailable, **record presence of detectable urinary bilirubin on dipstick**, indicating direct bilirubin elevations and suggesting liver injury
- Complete the liver imaging and/or liver biopsy eCRFs if these tests are performed

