7.1.4 Serious AE or SAR

An AE or SAR is considered serious if, in the view of either the investigator or sponsor, it results in any of the following outcomes:

- Death;
- Is life-threatening (places the subject at immediate risk of death from the event as it occurred);
- Requires inpatient hospitalization (>24 hours) or prolongation of existing hospitalization;*
- Results in congenital anomaly/birth defect;
- Results in a persistent or significant incapacity or substantial disruption of the ability to conduct normal life functions;

- Important medical events that may not result in death, be life-threatening, or require hospitalization may be considered a serious adverse drug experience when, based upon appropriate medical judgment, they may jeopardize the patient or subject and may require medical or surgical intervention to prevent one of the outcomes listed in the definition. For reporting purposes, also consider the occurrences of pregnancy as an event which must be reported as an important medical event.
- All events of possible drug-induced liver injury with hyperbilirubinaemia defined as ALT $\geq 3 \times \text{ULN}$ **and** bilirubin $\geq 2 \times \text{ULN}$ ($>35\%$ direct) (or ALT $\geq 3 \times \text{ULN}$ and INR >1.5 , if INR measured) or termed 'Hy's Law' events (INR measurement is not required and the threshold value stated will not apply to patients receiving anticoagulants). **NOTE:** bilirubin fractionation is performed if testing is available. If testing is unavailable, record presence of detectable urinary bilirubin on dipstick indicating direct bilirubin elevations and suggesting liver injury. If testing is unavailable and a subject meets the criterion of total bilirubin $\geq 2 \times \text{ULN}$, then the event is still reported as an SAE. If INR is obtained, include values on the SAE form. INR elevations >1.5 suggest severe liver injury.
- Any new primary cancers and treatment emergent malignancies (including squamous cell carcinoma and new primary melanoma) with the exception of basal cell carcinoma (BCC). BCC should be reported as an AE or SAE based on the discretion of the investigator.
- Symptomatic LVEF decrease that meets stopping criteria or asymptomatic LVEF decrease that does not recover, as outlined as LVEF guidance (Section 4.4.3.3)
- Retinal pigment epithelial detachment (RPED) or retinal vein occlusion (RVO)

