*Hospitalization for anticipated or protocol specified procedures such as administration of chemotherapy, central line insertion, metastasis interventional therapy, resection of primary tumor, or elective surgery, will not be considered serious adverse events.

In addition to the above, cases of fever with rigors or fever with hypotension should be reported as SAEs (regardless of whether or not hospitalization was required).

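### SAE instructions for RPED, complicated fever and Hy's Law in the toxicity sections do not match the SAE definition in 7.1.4, and non-serious liver stopping events have no current company recipient

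*Combined protocol and SAP*

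**What the plan says.** **RPED.** Section 7.1.4 includes "Retinal pigment epithelial detachment (RPED) or retinal vein occlusion (RVO") among serious events, with no grade attached. The 4.4.4 table treats the two conditions separately. At grade 1 its RPED instruction is "Continue treatment with retinal evaluation monthly until resolution", with no mention of SAE reporting, while RVO in the same row is to be reported as an SAE. At grades 2-3 the reporting instruction is again for RVO only: "Permanently discontinue study treatment and report RVO as SAE". At grade 4 it covers both: "If RVO or RPED diagnosed, permanently discontinue study treatment and report as SAE".

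**Fever.** Section 4.4.8 says: "Pyrexia accompanied by hypotension, dehydration requiring IV fluids, or severe rigors/chills should be reported as an SAE", and sends the reader to 7.3.3. Section 7.1.4 says: "cases of fever with rigors or fever with hypotension should be reported as SAEs", whether or not the patient was hospitalized. Section 5.2.7 repeats the 7.1.4 wording and cites 7.1.4.

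**Hy's Law.** The note in 4.4.9.1 reads: "Any case that meets these criteria and is considered to be drug related is considered to be an SAE by GSK". Section 4.4.9.2 requires every event meeting the laboratory thresholds to be reported as an SAE. Section 7.1.4 also defines the reportable event by those thresholds.

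**Recipient.** For any liver stopping event, 4.4.9.2 instructs: "Report the event to GSK", within 24 hours, citing 7.3.3. Section 11.4.1 directs requests for pharmacokinetic supplies to GSK as well. The only company named as recipient in 7.3.3 is Novartis, which supplies both drugs under 5.1.1 and 5.2.1.

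**The concern.** Investigators manage a toxicity from the tables in 4.4, so the SAE instruction there is likely to be the one they act on. The SAE call starts the 24-hour Oncore entry in 7.3.2 and the 24-hour company report in 7.3.3, and safety data go to the DSMC under 7.4. If the sections give different triggers, the SAE listing partly reflects which section was consulted. Most of the affected conditions belong to categories the protocol treats as adverse events of special interest for these drugs: ocular events, pyrexia and hepatic events. Separately, an instruction to report to a company that the reporting section no longer lists leaves part of the liver safety information without a valid route.

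**Working it through.** No plan figure is involved. The check sets each SAE instruction in 4.4 and 5.2.7 beside 7.1.4, and the liver reporting route beside 7.3.3.

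| Event | Toxicity section | 7.1.4 |
|---|---|---|
| RVO, any grade | SAE (4.4.4) | SAE |
| RPED, grades 1-3 | No SAE instruction (4.4.4) | SAE |
| RPED, grade 4 | SAE (4.4.4) | SAE |
| Fever with hypotension | SAE (4.4.8, 5.2.7) | SAE |
| Fever with severe rigors | SAE (4.4.8, 5.2.7) | SAE |
| Fever with rigors, not severe | Not listed in 4.4.8; SAE in 5.2.7 | SAE |
| Fever with dehydration needing IV fluids, no rigors or hypotension | SAE in 4.4.8; not listed in 5.2.7 | Not listed |
| Hy's Law values, judged not drug related | Outside the 4.4.9.1 note; SAE in 4.4.9.2 | SAE by laboratory definition |
| LVEF decrease (control) | SAE if symptomatic, or asymptomatic without recovery (4.4.3.3) | Same |

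1. **RPED.** The mismatch is at grades 1 to 3, where the table is silent. The silence carries weight because RVO is named for reporting in the same rows and RPED is added only at grade 4. The grades matter. Section 1.5.2 reports a 25% incidence of ocular events, all grade 1 or 2 except one grade 3 RPED. Appendix H shows 22 of 209 combination patients with ocular events in MEK115306, two at grade 3 and none at grade 4. In that experience, the table's only RPED reporting instruction would never have applied.

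2. **Fever.** The lists agree on hypotension and severe rigors. They differ on dehydration needing IV fluids (4.4.8 only) and on non-severe rigors (7.1.4 and 5.2.7 only). The cross-reference in 4.4.8 does not settle it, because 7.3.3 covers recipients and timing and holds no list of triggers.

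3. **Hy's Law.** The laboratory thresholds are the same in all three places. Only the 4.4.9.1 note adds causality. The Novartis text in 7.3.3 asks for every SAE whatever its suspected cause, so the note is the outlier.

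4. **Recipient.** Stopping criterion 1 is the Hy's Law combination. It is an SAE and reaches Novartis under 7.3.3. Criteria 2 to 5 rest on ALT level, persistence, symptoms or inability to monitor, and are SAEs only if they also meet 7.1.4. Section 4.4.9.2 itself allows for this by asking for the SAE form only when SAE criteria are also met. For a criteria 2-5 event that is not serious, the only company named is GSK, and the section cited for the route describes a Novartis duty limited to SAEs and pregnancies.

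5. **Control.** The LVEF triggers in 4.4.3.3 match 7.1.4, so the tables can carry a complete SAE instruction where one is intended.

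6. **Size.** Background rates applied to 20 patients give 20 × 0.11 = 2.2 to 20 × 0.25 = 5 with an ocular event, 20 × 0.51 = 10.2 to 20 × 0.76 = 15.2 with pyrexia, and 20 × 0.13 = 2.6 to 20 × 0.15 = 3 with a hepatic event. None of these counts the disagreement. The ocular figure includes blurred vision, dry eye and visual impairment, and the RPED share is not given. Section 4.4.8 says only that a minority of fever cases were complicated. That minority includes hypotension, which triggers in both lists, and dizziness or weakness, which trigger in neither; non-severe rigors fall outside it. The hepatic figure covers enzyme and bilirubin rises of any grade; grade 3 events in MEK115306 were 5%, or 20 × 0.05 = 1 patient.

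**The case against.** The strongest reply is that the sections add to one another. The 4.4.4 column gives actions and dose modifications, and nowhere says that RPED below grade 4 is not an SAE. Section 4.4 is not a complete SAE list: 4.4.2.2 is also silent on reporting new primary melanoma, which 7.1.4 lists. Neither fever list excludes the other's items, and 7.1.4 also captures hospitalization over 24 hours and important medical events. On Hy's Law, the action list in 4.4.9.2 already gives the 7.1.4 answer. Events not called serious are still recorded with grade in the eCRF under 7.2.

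Much of this stands. A reader might infer that 4.4.4 and 7.1.4 give RPED opposite SAE status at grades 1 to 3. They do not: one is silent and the other includes it, and a site that reads 7.1.4 in full would report every RPED. A reader might also infer that liver events go to GSK alone. The documents do not support that either, since every SAE must reach Novartis within 24 hours.

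What does not fall away is that someone working from one section alone would make a different SAE call from someone working from the other. This holds for RPED at grades 1-3, for the two fever presentations, and for a Hy's Law case judged unrelated if only the note is read. The recipient gap for non-serious liver stopping events is not closed by reading any other section.

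**Conclusion.** The point holds as a set of wording mismatches with a practical reporting consequence. RPED and fever are the substantive trigger mismatches; Hy's Law is minor and confined to one note. The recipient problem is real but limited to non-serious events under liver criteria 2 to 5.

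Two stronger conclusions are not supported. A reader might infer that one site will report an event and another will not; the documents show only that this may happen, and it could equally happen between investigators at one site. A reader might also turn the background rates into a number of affected patients; the documents do not give the shares needed, so no number is offered. The objectives in section 2 do not use SAE counts, so neither the kinome analysis nor response, PFS or survival is affected. The conclusion assumes that investigators may act on a toxicity table without checking 7.1.4. The correction is worth making because it concerns 24-hour safety reporting and is cheap.

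**What to change.** - Make 7.1.4 the single list of protocol-specified SAEs, and have 4.4.4, 4.4.8, 4.4.9.1 and 5.2.7 refer to it.
- State one RPED reporting rule there, making explicit whether it applies at every grade, as 7.1.4 now reads.
- Reconcile the fever lists into one, settling dehydration needing IV fluids and the severity of rigors, and correct the 7.3.3 cross-reference in 4.4.8.
- Remove the causality condition from the 4.4.9.1 note so that it matches 4.4.9.2 and 7.1.4.
- Replace GSK in 4.4.9.1, 4.4.9.2 and 11.4.1 with the recipient in 7.3.3, and state in 7.3.3 that all liver stopping events are covered, serious or not.

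These changes concern reporting only and need no change to any dose or treatment-stopping rule. The cost is a wording amendment, a memo to sites and possibly a few more SAE forms.
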